## BACKGROUND

The evolution, not only in technologies but also in the selection of patients, and the development of competences in peri-operative and post-operative management have led to a constant improvement in the survival of left ventricular assist device (LVAD) carriers.

However, after LVAD implantation, patient's functional capacity is still reduced with peak oxygen uptake ( $\text{VO}_2$  peak) values calculated by cardiopulmonary exercise testing (CPET) ranging from 11 to 20 mL/kg/min.

Various determinants have an influence on functional capacity. Only few previous reports have analysed the effects of pump speed increase on exercise performance in LVAD patients with contradictory results: an upgrade was observed in some, but not in all reports.

Moreover, the role of right ventricle (RV) is often underestimated: Murninkas et al. found a decrease in  $\text{VO}_2$  peak of 0.97 mL/kg/min for each ejection fraction reduction of the RV by 10%. A more favourable haemodynamic profile for the RV and a probable better response in terms of functional capacity can therefore be expected from LVAD echo-optimization (EO).

Uriel et al. demonstrated that EO can help patient management: in particular, the haemodynamic improvement was evident with an increase in cardiac output and a decrease in pulmonary capillary wedge pressure, confirmed by right heart catheterization.

We conduct a prospective randomized trial [The Effects of Echo-optimization of Left Ventricular Assist Devices on Functional Capacity, a RAndomized Controlled Trial (VAFRCT)] to evaluate the additional benefit of an EO approach on functional capacity measured by CPET and on quality of life in LVAD carriers.

## MATERIALS AND METHODS

### STUDY POPULATION

Subjects studied are patients supported with a continuous-flow LVAD: HeartMate II (Thoratec Inc., Pleasanton, CA) and HeartMate 3TM (Abbott, North Chicago, IL). All are ambulatory patients recruited by our Day Hospital of the Division of Cardiovascular Surgery at the University Hospital of Verona.

Inclusion criteria are as follows:

- enrolment at least 3 months after LVAD implantation;
- compliance to the required follow-up schedule;
- age  $\geq 18$ .

Exclusion criteria are as follows:

- distance of less than 150 m on the 6 min walking test or impossibility to perform CPET;
- poor acoustic window for echocardiographic imaging acquisition;
- recent finding of any major device-related complication (sepsis, thrombosis ...).

Patients are randomized with a 1:1 allocation (using random block sizes of 4 and 6) to EO (EO group) vs. standard settings (CONTROL group) after at least 3 months from the LVAD implantation. Randomization is performed using a web-based service with secured password and protected login, managed by a doctor not involved in the trial. The ordering of blocks and their respective size is unknown to the investigators.

Patients randomized to EO treatment performed echo-guided device programming at randomization. In CONTROL group, patients performed LVAD EO, but the optimal device speed is not confirmed at the end of procedure. The flow chart is specified in **Figure 1**.

The primary endpoint of our study is VO2 peak change at 3 months after the EO.

The secondary endpoints are as follows: right ventricular function (assessed by echocardiography and evaluated by fractional area change); device-related hospital admissions (complications are defined according to the Interagency Registry for Mechanically Assisted Circulatory Support); N-terminal pro-brain natriuretic peptide (NT-proBNP) levels; CPET exercise time and changes in quality of life perceived by the EuroQol Five Dimensions 3L questionnaire (EuroQol Group, Rotterdam, the Netherlands) and the Kansas City Cardiomyopathy Questionnaire.

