#### **ECHO-OPTIMIZATION PROCEDURE**

Complete transthoracic echocardiographic exams are performed in accordance with current American Society of Echocardiography guidelines, using a CX-50 xMatrix Philips cardiac ultrasound system (Philips S.p.A, Milan, Italy).

Before starting the procedure, blood pressure is recorded. The patient's device speed is lowered to the minimum speed clinically recommended. After 2 min, the following parameters are documented: left ventricular (LV) end-diastolic dimension, LV end-systolic diameter, frequency of aortic valve (AV) opening, degree of aortic regurgitation, degree of mitral regurgitation, right ventricular systolic pressure, blood pressure, and heart rate. Also, the other pump parameters are recorded (power, pulsatility index, and flow).

Left ventricular end-diastolic and end-systolic dimensions are measured from the parasternal long-axis view; AV opening is assessed using M-mode over the AV in the parasternal long-axis view. Visual estimation of the severity of aortic and mitral regurgitation is performed in the parasternal long-axis view using the colour Doppler imaging technique. For the assessment of aortic and mitral regurgitation, the degree is graded from 0 to 3 (0, none; 1, mild; 2, moderate; and 3, severe). Right ventricular systolic pressure is estimated from peak tricuspid regurgitation velocity using the modified Bernoulli's equation.

The recommended speed range varies according to the indications given in the data sheet for each specific device: for the HeartMate II, the clinical recommended range is between 8800 and 10 000, and the speed can be changed by an increment or reduction of 200 rpm; for the HeartMate 3TM, the

allowed speed is between 4800 and 6200 rpm with possible modifications of 100.

Therefore, the device speed is increased, at 2 min intervals with repeated acquisition of all echocardiographic and device parameters at each speed step, up to the maximum clinically recommended speed.

The optimal velocity is defined as the one that allows an intermittent AV opening and a neutral position of the interventricular septum without increasing aortic and/or tricuspid regurgitation, associated or not to a dilatation of the RV.

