## **STATISTICAL ANALYSIS**

The Student's t-test and the  $\chi^2$  test are used to compare groups at baseline for continuous and nominal data, respectively.

A paired t-test is used to assess within-group changes from baseline to 3 months. Analysis of covariance is used to compare the differences in change from baseline to follow-up between the two groups. Statistical significance is defined as  $P < 0.05$  (two-tailed).

Data are presented as mean  $\pm$  standard deviation unless otherwise stated. All statistical analyses are performed with IBM SPSS Version 22.0 (Armonk, New York).

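### Two pump models with different speed ranges are pooled, but neither the randomisation nor the ANCOVA names pump model: a minor, cheap gain in precision is left unused

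*Combined protocol and SAP*

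**What the plan says.** - **Population** (Study Population): "Subjects studied are patients supported with a continuous-flow LVAD: HeartMate II (Thoratec Inc., Pleasanton, CA) and HeartMate 3TM (Abbott, North Chicago, IL"). Both models form one trial population.
- **Randomisation** (Study Population): "Patients are randomized with a 1:1 allocation (using random block sizes of 4 and 6) to EO (EO group) vs. standard settings (CONTROL group"). The section also describes the web service and the concealment of block order and size. It mentions no stratification factor.
- **Pump settings** (Echo-Optimization Procedure): "for the HeartMate II, the clinical recommended range is between 8800 and 10 000", in steps of 200 rpm. The corresponding HeartMate 3 statement is "allowed speed is between 4800 and 6200 rpm with possible modifications of 100".
- **Primary endpoint** (Study Population): VO2 "peak change at 3 months after the EO".
- **Between-group analysis** (Statistical Analysis): "Analysis of covariance is used to compare the differences in change from baseline to follow-up between the two groups". No covariates are listed, so pump model is neither included nor excluded. Baseline comparisons use a t-test and a chi-square test.

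**The concern.** Pump model is not an arbitrary baseline characteristic here, because the pump delivers the intervention. From the stated ranges, one model offers 7 settings over 1200 rpm and the other 15 settings over 1400 rpm. The model is known before randomisation, so it could be balanced by design at almost no cost. It may also matter for device-related admissions, a secondary endpoint.

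With about 36 patients, a list without a pump stratum can leave the arms with different pump mixes. If 3-month VO2 peak change also differs by pump, the estimate from that particular allocation is displaced, and some precision is lost. Because the ANCOVA covariates are unlisted, pump could also be added or left out after results are known.

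**Working it through.** **Inputs from the documents.** Changes of 0.8 (SD 2.8) in control and 3.1 (SD 1.87) in the active group; two-sided alpha 0.05; power 80%; 18 per group (Sample Size Determination; Statistical Analysis). Speed ranges and steps are from the Echo-Optimization Procedure.

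**Assumptions.** The documents give neither the pump mix nor a pump effect on VO2 peak change. Mixes of 18/18, 12/24, 9/27 and 6/30 and effects of 0.5, 1 and 2 mL/kg/min are used to show a range.

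**1. The plan's own figure.**
- Difference: 3.1 − 0.8 = 2.3.
- Pooled variance: (2.8² + 1.87²)/2 = 5.67, so SD = 2.38.
- Standard error of the difference with 18 per arm: 2.38 × √(2/18) = 0.79.
- Noncentral t power: 78.0% at 17 per group and 80.4% at 18. The stated 18 per group reproduces.

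**2. Settings per pump.** HeartMate II: 1200/200 + 1 = 7. HeartMate 3: 1400/100 + 1 = 15.

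**3. Chance of a pump imbalance.** If K of 36 patients have one model, the number k in the EO arm is hypergeometric (36, K, 18), and the arms differ by |2k − K|.

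| Pump mix | Differ by ≥ 4 | Differ by ≥ 6 |
|---|---|---|
| 18/18 | 32% | 9% |
| 12/24 | 29% | 8% |
| 9/27 | 12% | 2% |
| 6/30 | 18% | 2% |

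With 9/27 only odd differences can occur, so its first column means at least 5. That is why it lies below the 6/30 row. The table treats the arms as exactly 18 and 18; simulating blocks of 4 and 6 changes it little.

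**4. Shift in the estimate.** Shift = (imbalance/18) × pump effect on change.

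| Pump effect (mL/kg/min) | Imbalance of 4 | Imbalance of 6 |
|---|---|---|
| 0.5 | 0.11 | 0.17 |
| 1 | 0.22 | 0.33 |
| 2 | 0.44 | 0.67 |

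The direction is random. All of these are below one standard error (0.79). If the pump difference arises only in the EO arm, an imbalance of 4 (for example 11 versus 7 of 18) moves that arm by 2/18 from an even mix, so the shift is about half: 0.11 for an effect of 1.

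**5. Validity.** In simulation (12,000 runs per scenario, blocks of 4 and 6, pump share 50%), the unadjusted estimate averaged 2.30 for a true 2.3. Type I error was 4.9% to 5.4% with or without a pump term. Given an imbalance of at least 20 percentage points, unadjusted type I error was about 6% for a pump effect of 1 and 9% for an effect of 2.

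**6. Power with 18 per arm, even mix.** The pump contributes variance 0.25 × effect². The answer depends on whether the planned SD already contains it.
- *Added to the planned variance.* Effect 1: 5.67 + 0.25 = 5.92, unadjusted power 79%. Effect 2: 5.67 + 1 = 6.67, unadjusted power 74%.
- *Already inside the planned SD.* Unadjusted power stays near 80%. In simulation a pump term left it at 81% for effect 1 and raised it from 81% to 87% for effect 2.
- *No pump effect.* A pump term without stratification took simulated power from 81% to 80%.

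**The case against.** The strongest reply is that nothing in the documents shows that the pump affects the 3-month change. Different rpm scales do not show it: 1200/8800 = 14% and 1400/4800 = 29% describe each device's own scale, with no conversion to flow or VO2. Both pumps are also set to the same echocardiographic targets. Because the endpoint is a change, a pump difference in VO2 peak level is largely removed. This stands, and it is why every size above rests on an assumed effect.

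A second reply concerns mechanism. In the control arm the optimal speed is not retained, so a difference in speed range could act mainly in the EO arm. That would be effect modification, which a main-effect pump term does not model. This also stands; the term handles only a pump difference common to both arms.

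Third, no pump stratum and no pump term are readings of silence, and leaving a single-centre trial of 36 unstratified is a legitimate choice. That is fair. However, the randomisation is otherwise described in detail, and a baseline chi-square test can display an imbalance but not adjust for it.

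A reader might infer that any pump imbalance passes in full into the EO effect, or that the comparison is biased. The documents do not support this: only imbalance times pump effect on change carries over, and randomisation keeps the overall test valid. Nor can a fall in power to 74% be taken as a finding. It needs a 2 mL/kg/min pump effect added on top of the planned SD, and the Sample Size Determination section does not say whether its SDs are within pump.

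**Conclusion.** A minor point that holds as an improvement to the design, not as an error that invalidates the analysis. Two pumps that deliver the intervention over different ranges and steps are pooled, and the plan does not use this known factor in randomisation or analysis.

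An imbalance of at least 4 of 18 is plausible (12% to 32% across the mixes shown). Its effect ranges from negligible to roughly half a standard error at an imbalance of 4 (0.44/0.79 = 0.56), for pump effects up to 2 mL/kg/min. The possible gain in power is nil to about 6 points. Both rest on assumed pump mixes and effects. The sample size does not change.

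**What to change.** - **If recruitment has not started:** run the existing blocks of 4 and 6 as two lists, one per pump model, in the web service, and prespecify pump model as a fixed factor in the VO2 peak ANCOVA.
- **If patients are already randomised:** prespecify the factor only, before results are seen.
- **In either case:** list all ANCOVA covariates in the Statistical Analysis section. Report the EO effect by pump descriptively. With an even mix that is about 9 patients per arm and pump, so these estimates will be imprecise and should not be tested.

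Cost: one setting in the existing service, one model term and one degree of freedom (about one power point if the list is unstratified and pump has no effect). Incomplete last blocks in two strata can leave the arms a few patients apart, more noticeably if one pump is rare.

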## **SAMPLE SIZE DETERMINATION**

Kerrigan et al. proposed a design similar to our protocol, with the intention, however, of verifying the contribution of another tool (rehabilitation) to improve the functional capacity of LVAD patients. It has been hypothesized that the EO group undergoes a variation equal to the rehabilitated group reported by Kerrigan, while the non-optimized group behaves like the control group of that study. Because the study did not report the standard deviation of the differences, it is estimated taking into account the correlation between the two measurements, according to the value of  $r = 0.50$ , as suggested by the Cochrane Heart Group. Therefore, a variation is obtained for the control group of  $0.8 \pm 2.8$  and for the 'active' group of  $3.1 \pm 1.87$ . Assuming an alpha value of 0.05 and a power of 80%, an estimated sample size of 18 patients for each group is obtained.

## **STUDY PROCEDURES**

### **MEASUREMENT OF BLOOD CHEMISTRY AND HAEMATOLOGIC VARIABLES**

Fasting blood samples are collected at baseline and at 3 months to assess parameters of haemolysis (lactate dehydrogenase and haptoglobin) or infection (complete blood count and high sensitivity C-reactive protein) and to investigate kidney (creatinine and blood urea) and liver function (bilirubin and alanine and aspartate aminotransferase). Lipid profile (low-density lipoprotein, high-density lipoprotein, and total cholesterol, triglycerides), blood glucose, and serum electrolytes (sodium and potassium) were also measured. Dosage of NT-proBNP, as secondary endpoint of our study, are included in the evaluation. Lastly, measurement of prothrombin time–international normalized ratio are fundamental to allow our procedure of EO in safe conditions (a value at least  $>1.8$  was requested).

### **CARDIOPULMONARY EXERCISE TEST**

For the exercise test, a bicycle ergometer is used (Quark CPET, COSMED, Rome, Italy). Respiratory gas exchange measurements are obtained breath-by-breath (Omnia 1.6.5, COSMED, Rome, Italy) using a face-mask as patient/metabolic cart interface.

The aim of the exercise duration is  $10 \pm 2$  min. In all patients, the initial workload is 10 W, and it was gradually increased by a 10 W/min ramp until patients reached exhaustion. The protocol is not changed between baseline and 3 months CPET. Patients are motivated to put their maximal effort

thus allowing a reliable measurement of  $\text{VO}_2$  peak, calculated in mL/kg/min. We considered the highest 30 s average  $\text{VO}_2$  value over the last minute of the exercise phase. Minute ventilation/ $\text{CO}_2$  production slope is calculated as the slope of the linear relationship between minute ventilation and  $\text{CO}_2$  production form excluding the initial part of the test (potentially influenced by hyperventilation) and the final part (from the end of the isocapnic tamponade to the end of the exercise). The anaerobic threshold is measured with the V-slope analysis from the plot of  $\text{CO}_2$  output vs.  $\text{O}_2$  uptake on equal scales. This value is confirmed analysing ventilatory equivalents and end-tidal pressures of  $\text{CO}_2$  and  $\text{O}_2$ . A respiratory exchange ratio  $>1.05$  is used as an indicator of an adequate performed test.

#### **ECHO-OPTIMIZATION PROCEDURE**

Complete transthoracic echocardiographic exams are performed in accordance with current American Society of Echocardiography guidelines, using a CX-50 xMatrix Philips cardiac ultrasound system (Philips S.p.A, Milan, Italy).

Before starting the procedure, blood pressure is recorded. The patient's device speed is lowered to the minimum speed clinically recommended. After 2 min, the following parameters are documented: left ventricular (LV) end-diastolic dimension, LV end-systolic diameter, frequency of aortic valve (AV) opening, degree of aortic regurgitation, degree of mitral regurgitation, right ventricular systolic pressure, blood pressure, and heart rate. Also, the other pump parameters are recorded (power, pulsatility index, and flow).

Left ventricular end-diastolic and end-systolic dimensions are measured from the parasternal long-axis view; AV opening is assessed using M-mode over the AV in the parasternal long-axis view. Visual estimation of the severity of aortic and mitral regurgitation is performed in the parasternal long-axis view using the colour Doppler imaging technique. For the assessment of aortic and mitral regurgitation, the degree is graded from 0 to 3 (0, none; 1, mild; 2, moderate; and 3, severe). Right ventricular systolic pressure is estimated from peak tricuspid regurgitation velocity using the modified Bernoulli's equation.

The recommended speed range varies according to the indications given in the data sheet for each specific device: for the HeartMate II, the clinical recommended range is between 8800 and 10 000, and the speed can be changed by an increment or reduction of 200 rpm; for the HeartMate 3TM, the

allowed speed is between 4800 and 6200 rpm with possible modifications of 100.

Therefore, the device speed is increased, at 2 min intervals with repeated acquisition of all echocardiographic and device parameters at each speed step, up to the maximum clinically recommended speed.

The optimal velocity is defined as the one that allows an intermittent AV opening and a neutral position of the interventricular septum without increasing aortic and/or tricuspid regurgitation, associated or not to a dilatation of the RV.

The test is stopped in case of a decrease in LV end-diastolic diameter  $\leq$  3 cm, suction events, ventricular arrhythmias, symptoms (palpitations, dizziness, dyspnoea, chest pain, or headache), hypertension (mean artery pressure  $>$  100 mmHg), and hypotension (mean artery pressure  $<$  60 mmHg). At the end of the exam, a new assessment of blood pressure is performed, and the images recorded are reviewed.

## **STATISTICAL ANALYSIS**

The Student's t-test and the  $\chi^2$  test are used to compare groups at baseline for continuous and nominal data, respectively.

A paired t-test is used to assess within-group changes from baseline to 3 months. Analysis of covariance is used to compare the differences in change from baseline to follow-up between the two groups. Statistical significance is defined as  $P < 0.05$  (two-tailed).

Data are presented as mean  $\pm$  standard deviation unless otherwise stated. All statistical analyses are performed with IBM SPSS Version 22.0 (Armonk, New York).

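### Do the within-arm paired t-tests let an ineffective echo-optimization pass as effective?

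*Combined protocol and SAP*

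**What the plan says.** The Statistical Analysis section lists three kinds of comparison.

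- Baseline: Student's t-test and the chi-square "test are used to compare groups at baseline for continuous and nominal data, respectively".
- Within arm: "A paired t-test is used to assess within-group changes from baseline to 3 months".
- Between arms: "Analysis of covariance is used to compare the differences in change from baseline to follow-up between the two groups".

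A single two-sided threshold of P < 0.05 covers all of them. The section does not name the analysis of covariance (ANCOVA) as the primary analysis of peak VO2, does not state its covariates, and does not label the paired tests descriptive.

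The Sample Size Determination section supplies the expected changes. "Therefore, a variation is obtained for the control group of" 0.8 ± 2.8, against 3.1 ± 1.87 in the EO arm. It concludes: "Assuming an alpha value of 0.05 and a power of 80%, an estimated sample size of 18 patients for each group is obtained".

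The Study Population section words the primary endpoint as the change in peak VO2 three months after EO. The Background gives the aim as evaluating the added benefit of an EO approach.

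**The concern.** A paired test in the EO arm asks whether patients changed over three months, not whether EO caused the change. The plan's own assumption for non-optimised patients is a gain of 0.8, so its null hypothesis of zero change is expected to be false even if EO is useless. A result that is significant in the EO arm and not in the control arm is not a test of the difference between arms.

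Two features of the text add to the worry. The primary endpoint is worded as a change rather than a between-arm difference, so the EO-arm paired test could seem to address it. The paired tests also share the ANCOVA's threshold, and neither is ranked above the other. With 18 patients per arm, a report could stress a within-arm pattern while the randomised comparison was null.

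The baseline significance tests raise a lesser point. After proper randomisation any baseline difference is due to chance, so those P values answer no useful question.

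**Working it through.** **Inputs.** From Sample Size Determination: control change 0.8, SD 2.8; EO change 3.1, SD 1.87; 18 per arm; alpha 0.05; power 80%. From Statistical Analysis: two-sided testing. Assumed here: normally distributed changes and all 18 per arm analysed.

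**1. What the sample size is built on.**
- Difference: 3.1 − 0.8 = 2.3.
- Pooled SD: √[(2.8² + 1.87²)/2] = 2.381.
- Noncentrality at 18 per arm: 2.3 / (2.381 × √(2/18)) = 2.90, on 34 df.
- Power from the noncentral t: 78.0% at 17 per arm and 80.4% at 18. The Welch version gives 80.0% at 18. The normal approximation gives 17 per arm.

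The stated 18 per arm is reproduced, and it comes from a comparison between arms. A paired test plays no part in it.

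**2. Paired test in the EO arm when EO has no effect.** The true mean change is 0.8, with 17 df. The noncentrality is 0.8 × √18 / SD, and improvement is declared when t > 2.11.

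| SD of change | Noncentrality | Probability of significant improvement |
|---|---|---|
| 2.8 | 1.21 | 20.7% |
| 1.87 | 1.82 | 40.2% |

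The test's nominal rate in that direction is 2.5%, but that applies only when the true change is zero. With 16 analysed per arm the range is 18.7% to 36.0%.

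**3. EO significant for improvement, control not.** The arms are independent, so the probability is P(EO significant) × [1 − P(control significant)].

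| SD in EO / control | Calculation | Result |
|---|---|---|
| 2.8 / 2.8 | 0.207 × 0.793 | 16.4% |
| 1.87 / 1.87 | 0.402 × 0.598 | 24.0% |
| 1.87 / 2.8 | 0.402 × 0.793 | 31.9% |

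By simulation, this pattern occurs together with a non-significant between-arm test in about 14% of trials in the first row and about 30% in the last.

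**4. Between-arm test in the same setting.** By simulation, a two-sample t-test on change, standing in for ANCOVA, rejects in about 5% of trials under each SD pairing, and in favour of EO in about 2.5%.

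**5. Which row fits the premise.** If EO does nothing, EO patients should behave like controls, whose SD is 2.8. The coherent figures are therefore 21% and 16%. The 40% and 32% remove the active arm's effect but keep its SD.

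**6. Whether leaving the covariate unstated matters.** The natural covariate for an ANCOVA of change from baseline is the baseline value. Write the model as (Y₃ − Y₀) = a + b·arm + c·Y₀. Moving Y₀ to the right gives Y₃ = a + b·arm + (c + 1)·Y₀. The treatment coefficient b is the same whether change or the three-month value is the outcome.

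**The case for a change.** The strongest case for a change is that the text leaves two routes to a significant result and closes neither. The endpoint is worded as a change, no test is named as primary, and one threshold covers everything. On the plan's own figures, the within-arm route would favour a useless intervention several times more often than 5%. Two sentences of wording would close that route at no cost in data or patients.

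The arithmetic stands, and so does the observation that the plan neither ranks the tests nor labels the paired ones descriptive. Other parts are weaker.

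- Calling 21% or 40% a false-positive rate is inaccurate. If the true change within the arm is 0.8, rejecting zero change is a correct decision. It becomes an error only when someone reads it as an effect of EO, and the section assigns the paired test no such role.
- The section names no endpoints, so the concern cannot be extended to all of them. Device-related hospital admissions have no baseline measurement described and do not suit a paired t-test.
- Regression to the mean finds no support in the eligibility criteria. They exclude patients who walk less than 150 m and do not select for low peak VO2.
- The baseline tests trigger no decision, such as choosing covariates. They are redundant but harmless to the treatment comparison.

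**Conclusion.** No change to the plan is needed. Followed as written, it gives a sound randomised comparison: ANCOVA between arms at two-sided 0.05, in a trial sized on the between-arm difference of 2.3. The paired tests are described only as assessing change within a group, and no section makes efficacy depend on them.

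If they were misread as evidence of efficacy, an ineffective EO would appear significantly improved in about 21% of trials, and the split pattern would appear in about 16%. The upper figures of 40% and 32% require the active-arm SD. All of these assume a 0.8 gain in both arms, 18 analysed per arm and normally distributed changes. The 0.8 is borrowed from the control arm of a rehabilitation trial and was not observed in this population.

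Naming ANCOVA as primary, with baseline peak VO2 as covariate, would record what a competent analyst would do from the present text. Removing the paired or baseline tests would alter no treatment-effect estimate, interval or P value. The practical lesson is for reading the report: judge efficacy on the between-arm result and treat within-arm P values as description.

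### Does silence on low-RER tests, analysis population and missing 3-month tests make the between-group ANCOVA unsound?

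*Combined protocol and SAP*

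**What the plan says.** The primary endpoint (Study Population) is VO2 "peak change at 3 months after the EO", so each patient needs a usable exercise test at baseline and at 3 months.

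The Cardiopulmonary Exercise Test section defines the measurement once, with no condition on RER: "We considered the highest 30 s average" of VO2 in the last minute of exercise. It says "Patients are motivated to put their maximal effort" and links that effort to a reliable value. An RER above 1.05 "is used as an indicator of an adequate performed test", and no consequence is attached to a lower value. The same procedure serves both visits: "The protocol is not changed between baseline and 3 months CPET".

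The Statistical Analysis section gives the comparison of arms in one sentence: "Analysis of covariance is used to compare the differences in change from baseline to follow-up between the two groups". It adds the two-sided 5% level and the software. It states no analysis population, covariate or missing-data rule.

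Two entry criteria bear indirectly on the matter. Patients are excluded for "impossibility to perform CPET", and they must be able to keep to the follow-up visits. Under Sample Size Determination, "an estimated sample size of 18 patients for each group is obtained", with no stated allowance for lost or unusable tests.

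**The concern.** A threshold with no consequence invites a decision later. Three rules can be defended from the text:

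- keep every test, because the endpoint is defined for every test;
- drop patients whose 3-month test has RER at or below 1.05;
- drop patients with such a test at either visit, because the endpoint is a change and the text links reliability to maximal effort.

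If someone chose among these after seeing the results, the error rate would no longer be 5%. Dropping by 3-month RER also selects patients on something measured after randomisation. With 18 per arm, one or two patients can move a p value across 0.05. A missing 3-month test raises the same question: if losses were related to outcome in one arm, an analysis of observed changes would be biased.

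**Working it through.** **1. The plan's own figure.** Inputs from Sample Size Determination: changes of 0.8 (SD 2.8) and 3.1 (SD 1.87), alpha 0.05, power 80%. Difference = 3.1 − 0.8 = 2.3. Common SD = √((2.8² + 1.87²)/2) = √5.668 = 2.38. The normal formula 2 × (SD × (1.960 + 0.842)/2.3)² gives 16.8, so 17 per arm. The exact two-sided t-test gives power 78.0% with 17 and 80.4% with 18. The stated 18 is reproduced.

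**2. What ANCOVA adds.** The plan assumes r = 0.50. With equal SDs at both visits (my assumption), the SD of the change equals the SD of one measurement, since √(2 × (1 − 0.50)) = 1. Adjusting for baseline leaves a residual SD of 2.38 × √(1 − 0.50²) = 2.06. Simulated ANCOVA power at a true effect of 2.3 is then 89% with 36 patients. With 2, 4, 6 or 8 of the 36 lost at random it is 87%, 85%, 82% or 79%.

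**3. Each rule fixed in advance.** In 100,000 simulated null trials with patients flagged at random, keeping all tests rejects in 4.9% to 5.0% and excluding flagged patients in 5.0% to 5.1%. Neither rule is wrong in itself.

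**4. Choosing afterwards.** The documents give no low-RER rate, so the rates are assumed, independent between visits and unrelated to arm. Ranges in the last column are over repeated simulations.

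| Low-RER rate per test | Patients with at least one, of 36 | Smaller p: keep, or drop on 3-month test | Smallest p of all three rules |
|---|---|---|---|
| 3% | 36 × (1 − 0.97²) = 2.1 | 5.6% | 6.2–6.4% |
| 5% | 36 × (1 − 0.95²) = 3.5 | 5.9% | 6.6–7.0% |
| 10% | 36 × (1 − 0.90²) = 6.8 | 6.5% | 7.7–7.9% |

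The last column assumes that the most favourable result is reported every time.

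**5. Is one RER rule clearly better?** Take a true effect of 2.3, with low-RER tests under-reading VO2 peak by a fixed amount at both visits.

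- No under-reading: keeping all tests has 89% power. Exclusion at either visit has about 85% (5% rate) or 80% (10% rate).
- Under-reading by 3 mL/kg/min: keeping all has 86.0% or 82.2%. Dropping on the 3-month test alone has 86.9% or 83.9%.
- Under-reading by 5: keeping all has 79% or 72%. Exclusion at either visit has about 85% or 81%.

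Now let the 3-month low-RER rate be 5% in the echo-optimised arm and 15% in control. With under-reading by 3, keeping all tests is biased by (0.15 − 0.05) × 3 = +0.30 mL/kg/min, with 6.6% error. With under-reading by 5, the arithmetic gives +0.50 (simulated +0.49), with 8.2% error. Dropping those tests gave no bias and 5% error in that setting. The preferred rule therefore depends on facts that the documents do not supply.

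**6. Missing 3-month tests.** If the echo-optimised arm loses 2 patients at random, the analysis of observed changes has no bias and about 5% error. If it loses 2 at random from the lower half of its changes, bias is +0.17 with 5.3% error. If it loses exactly its 2 worst changes, bias is +0.37 with 9% error. The last case is an extreme illustration, and nothing in the plan leads to it.

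**The case for a change.** The best argument for a change is that pre-specification costs a few sentences, while the trial is small enough for the choice to matter. At a true effect of 2.3, with 2, 4 or 8 of 36 patients flagged, keeping and excluding disagree on significance in about 4%, 7% or 13% of trials. The sample size has no stated reserve: by the t-test, 16 evaluable pairs per arm give 75.3% power.

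Part of this stands. The rule is not written down in the text available, and the entry criteria do not govern tests after randomisation.

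The rest does not carry the point. Two valid analyses of overlapping data will sometimes fall on opposite sides of 0.05, and that shows no defect in either. The t-test figure understates the planned ANCOVA, which on the plan's own correlation stays above 80% power with 6 of 36 patients lost at random (step 2). The error inflation arises only if someone sets aside the plain reading after seeing the data. The text calls RER an indicator and nowhere orders an exclusion.

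The possible remedies are not clear gains either. Naming baseline VO2 peak and the patients as randomised would record what an ANCOVA of change in a randomised trial already implies. Fixing keep-all as primary is a trade-off (step 5). Multiple imputation with shifts of 0 to 5 mL/kg/min would be a heavy addition for 18 per arm, and the documents give no source for that range.

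**Conclusion.** The concern does not call for a change. The silence is real in the text available. The front matter and the Figure 1 flow chart could not be checked, so a rule stated there cannot be ruled out. It is a gap in detail, not a faulty instruction: an analyst following the plan would compare all observed changes, as randomised, by ANCOVA with baseline VO2 peak as covariate. That analysis holds 5% error when low RER and missing tests are unrelated to arm and outcome.

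The exposure from choosing afterwards is about 1 to 3 percentage points of false-positive rate at assumed low-RER rates of 3% to 10% per test, and only if the smallest of three p values is always reported. Larger effects need stronger assumptions that the documents do not support: low-RER rates that differ threefold between arms with marked under-reading, or loss of exactly the worst patients from one arm. ANCOVA is read here as the primary analysis because it is the only between-arm comparison of change that the plan names.
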